cardiac death⁴⁵⁻⁴⁹. Fractal analysis of metabolomic data will allow us to test whether the Hurst exponent is related to clinical outcomes and/or response to nutritional interventions in the ICU patients we propose to study.

Emerging data strongly suggest that microbes of the intestine (the microbiota) play a key role in host metabolism, immune/inflammatory processes and disease pathophysiology⁵⁰⁻⁵². The intestinal microbiome (genome of the gut microbiota) is shaped by both environment (e.g. diet) and host genetics; and, vice versa, the gut microbiota itself appears to regulate a wide spectrum of host immune, inflammatory and metabolic responses⁵³. **Human data on the impact of nutrition support during critical illness on the gut microbiome are limited.**

Despite limited evidence, there is a suspected interplay between critical illness and the gut microbiome, which warrants further exploration in the setting of nutrition support⁵⁴⁻⁵⁸. Nelson et al utilized 16S rRNA pyrosequencing to characterize stool of hospitalized patients and observed perturbations in gut microbiota following infection⁵⁹. It is acknowledged that the microbiome plays an integral role in health maintenance, and that modifications of the gut microorganisms may influence outcomes in critically ill patients.

Hypothesis:

- 1) Adequate energy administration (defined as 1.3 x REE) will result in a lower 28-day total hospital-acquired infection rate compared with ICU patients receiving lower energy doses.
- 2) Differences in energy intake will result in global changes in metabolic patterns that themselves are associated with clinical outcomes in the ICU patients studied.

Specific Aims:

- 1) To perform a controlled, double-blind, prospective, randomized, parallel group, intent-to-treat Phase II clinical trial to test the efficacy of three specific energy doses [0.6, 1.0 and 1.3 x measured REE (metabolic cart), respectively], given for 28 consecutive days during the ICU course, on 28-day total hospital-acquired infections (primary endpoint), BSI, and other important clinical outcomes in medical/surgical ICU patients requiring specialized parenteral ± enteral feeding.
- 2) In Aim 1 subjects to: a) examine the impact of cumulative and mean daily 28-day energy deficits [energy intake-measured REE] on clinical outcome endpoints; and b) to estimate the agreement for REE as determined by the HBE and the measured REE across different energy doses.

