Study Schema: Controlled, randomized, double-blind, prospective, parallel-group, intent-to-treat **Aim 1** clinical trial to test the efficacy of three energy doses [0.6, 1.0, and 1.3 x measured REE (MREE), by metabolic cart, respectively], given for 28 consecutive days during the ICU and post-ICU course in critically ill medical and surgical patients requiring parenteral nutrition (PN) ±enteral nutrition (EN) at Emory University. The primary endpoint is total hospital-acquired infections after entry; secondary endpoints are bloodstream infections, ventilator-free days, and ICU and 28-day hospital length of stay and mortality. **Aim 2** examines the effect of cumulative and mean daily measured 28-day energy deficits after entry on Aim 1 clinical outcome endpoints and relationships between estimated REE (Harris-Benedict equation) at study entry. **Aim 3** explores the impact of energy dose and cumulative and mean daily 28-day energy deficits on global metabolomic patterns, microbiome, and strength over time and in association with key clinical outcomes in Aim 1.

↑ Plasma (metabolome), microbiome, and strength analysis

Data Collection: Baseline data collected will include APACHE II score, and clinical and demographic data. The following will be collected during the course of the study:

A) Measured resting energy expenditure (MREE; per metabolic cart) will be determined on the baseline day before 2 pm. The goal energy dose composition of PN for all three energy doses for each enrolled subject is calculated by the blinded research team members. The metabolic cart-derived REE will be used to determine basal energy expenditure (REE) and thus the initial energy dosing^{5, 10, 12}. MREE will be determined at baseline and 5x weekly (M-F before 2 pm; see Aim 2) using a state-of-the-art metabolic

cart and standard methodologies by a study team respiratory technician with prior experience and expertise in clinical indirect calorimetry. In the event that the metabolic cart is not available, the most recent measurements will be used. The nutrition will not be adjusted if the MREE is <10% changed from the reading the day before.

- B) Longitudinal SOFA scores of organ dysfunction/failure: Sequential organ failure assessment (SOFA) scores will be calculated in the morning of each ICU day ⁶⁰. The baseline Apache II score on the day of ICU admission will also be calculated in all patients.

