standardized CRFs. The primary endpoint is total nosocomial infection rate during the 28-day study period. Secondary Aim 1 post-entry endpoints to be monitored include: 1) 28-day hospital mortality; 2) Rate of new nosocomial blood stream infections (BSIs) during the initial 28 days; 3) Rate of new nosocomial infections during the initial 28 days; 4) mean ICU SOFA score; 5) ICU ventilator-free days at day 28; 6) ICU and total hospital length of stay.

Hospital nutrition support - Administration of double blind parenteral and enteral nutrition:

Briefly, the nutritional goals are to provide total daily calorie (kcal) intake [from PN + dextrose-containing IV fluids (> 500 mL/day) + propofol/clevidipine + any enteral feedings) at 0.6, 1.0 or 1.3 x baseline MEE (per metabolic cart). We will then serially adjust total PN/EN energy dosing based on real-time serial cart REE measurements during the ICU stay, as indicated by the energy dose group to which the patient is randomized. The total amino acid/protein intake goal is 1.2 g/kg/day. Dextrose will initially comprise 70% of PN non-amino acid kcal and IV fat (30% Intralipid[®]) 30% of PN non-amino acid kcal daily, adjusted as clinically indicated. The 1.0 x REE energy dose study group will serve as the control group in this CER study. Study PN will be continued only if deemed indicated by the investigators and the primary physicians. Daily intake of study PN volume (mL), PN dextrose (g), PN lipid emulsion (g), intake of study tube feeding volume, and daily PN and enteral (oral or tube feeding) volumes will be calculated and entered into the CRFs daily for the initial 28 days after entry, beginning on day 1.

Study subjects will receive a maximum of 28 days of double blind study PN ± EN. Subjects will be transitioned from PN to enteral feeds as soon as tolerated and clinically indicated. Study PN will be discontinued when enteral intake of \geq 50% of energy requirements is achieved for \geq 48 hr. The amount of PN administered will be decreased as a function of actual enteral nutrient intake to maintain daily goals. The 24-hr daily study PN will be prepared under sterile laminar air flow hood conditions by the unblinded research pharmacist and pharmacy technician at each site. The study EN will be made in the Metabolic Kitchen or in the compounding area of the pharmacy.

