Determination of energy deficit: Energy intake from PN \pm EN (tube feeds + any oral diet) will be determined as outlined in Aim 1 each day for the initial 28-days of study. MREE will be determined by metabolic cart 5x week (Monday through Friday) before 2 pm. Any PN or EN being administered will be continued uninterrupted during MREE determinations. The 5 daily cart measurement results (kcal/day) for each study week will be averaged and that mean daily value used as the daily measured energy requirement for all 7 days of that week. The daily energy deficit will be calculated by subtracting the calculated mean daily MREE during each study week from the actual daily energy intake. The cumulative and mean daily ICU and 28-day energy deficits will be determined. Metabolic cart measurements will not be performed on any given day in patients whom are in isolation due to resistant microorganism infection (contraindicated), or if the patient requires a fraction of inspired oxygen of < 60%, has a requirement for positive end-expiratory pressure of > 12 cm H₂O, or has a documented leak in the ventilator or chest tube systems (precluding accurate cart measurements) ^{32, 33}. The estimated REE by the HBE(outlined in detail in Table 3 of reference 3 ⁶¹) will be calculated on the baseline day using most recent available pre-ICU dry body weight.

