Data and Safety Monitoring Board (DSMB): The Data and Safety Monitoring Board (DSMB) will act in an advisory capacity to the National Institute of Diabetes, Digestive and Kidney Diseases (NIDDK) to monitor subject safety and evaluate the efficacy of the intervention being studied in this clinical trial funded by the NIDDK. The DSMB will be appointed by the PIs upon study funding, and approved by NIDDK program staff. The DSMB will be composed of at least two experienced clinical nutrition support investigators not otherwise participating in the study and not affiliated with Emory. A biostatistician not otherwise participating in the study will also be named to the DSMB. The DSMB will meet twice yearly, and as needed, and will receive blinded and unblinded reports on study progress prepared by the DCC.

Statistical Analysis:

Continuous variables will be summarized with standard descriptive statistics and represented graphically with displays such as scatterplots, box plots, line plots and histograms, while categorical variables (adverse events) will be described by frequency tables.

For Aim 1: The primary analyses of the data will be performed according to subjects' original treatment assignment (i.e., intention-to-treat analyses) and the inclusion of all data from all subjects randomized in the final analysis. Rates of infection (i.e., BSI and total nosocomial infections) per 1000 hospital days will be estimated overall and for each of the 3 energy doses. Confidence intervals (95%) for the incidence rates will be estimated using an exact method based on the Poisson distribution.

Additionally incidence rates of infection will be estimated by performing a generalized estimating equations (GEE) Poisson regression analysis of the counts, implemented using SAS Proc Genmod, using an exchangeable correlation structure for the repeated counts within subject. The incidence rate ratio (IRR) is the ratio of the incidence density in one group to that of another group. Results by each baseline covariate will be presented as the IRR and the 95% confidence interval (CI). This GEE model can also accommodate time-dependent covariates such as daily blood glucose levels measured before an infection and total 28-day energy (cumulative deficit or as a time-dependent covariate).

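### A daily energy deficit scored against a weekly mean lets post-infection cart readings alter the deficit on earlier days, which can bias any time-dependent deficit–infection analysis

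*Combined protocol and SAP*

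**What the plan says.** Determination of energy deficit takes the five weekday cart readings of a study week; these are "averaged and that mean daily value used as the daily measured energy requirement for all 7 days of that week". Then "The daily energy deficit will be calculated by subtracting the calculated mean daily MREE during each study week from the actual daily energy intake", and "The cumulative and mean daily ICU and 28-day energy deficits will be determined".

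Feeding follows a different clock. Under Hospital nutrition support, the team will "serially adjust total PN/EN energy dosing based on real-time serial cart REE measurements". Under Data Collection, item A, nutrition stays unchanged if the reading moves by less than 10% from the day before, and "In the event that the metabolic cart is not available, the most recent measurements will be used".

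The deficit has two uses. Specific Aim 2a is to "examine the impact of cumulative and mean daily 28-day energy deficits [energy intake-measured REE] on clinical outcome endpoints". The Statistical Analysis text for Aim 1 says that the infection GEE can accommodate time-dependent covariates, among them "total 28-day energy (cumulative deficit or as a time-dependent covariate". The same sentence limits glucose to "daily blood glucose levels measured before an infection" but sets no such limit for the deficit. The analysis text for Aim 2 covers only agreement between the Harris-Benedict estimate and measured REE, and an ANCOVA on that relationship. The GEE sentence is therefore the only place in the Statistical Analysis section that relates energy deficit to a clinical outcome.

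**The concern.** A time-dependent covariate should contain only what was known by the day it describes. Here Monday's requirement depends on Friday's reading. If an infection begins midweek and shifts REE, the later readings move the requirement for infection-free days on which feed was ordered from earlier readings. The recorded deficit before the infection is then partly a product of the infection. A one-day lag does not cure this, because the lagged value already contains the later readings of its week.

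At stake is whether a deficit reported as preceding infection can be read as such. That matters in a pilot meant to inform larger trials.

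**Working it through.** The plan states no power, effect size or event rate for the deficit analysis, so it has no figure to reproduce.

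**Inputs from the documents.** 60 patients in three arms of 20; multipliers 0.6, 1.0 and 1.3; 28 days; Monday–Friday readings; the 10% rule for adjusting nutrition; Poisson GEE with exchangeable correlation; two-sided tests.

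**Assumed.** REE 1800 kcal/day; REE change after infection of −10% to +30%; about 3 infections per 100 patient-days; alpha 0.05. The Background says only that energy needs vary with clinical condition.

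**Algebra.** If *k* of five readings follow the infection and REE changes by a proportion *r*, each pre-infection deficit that week shifts by −REE × *r* × *k*/5.

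- *r* = 0.15, *k* = 2: weekly mean (3 × 1800 + 2 × 2070)/5 = 1908. A patient fed exactly 1800 is recorded as 1800 − 1908 = −108 kcal/day.
- *r* = 0.15, *k* = 1: −1800 × 0.15 × 1/5 = −54.
- *r* = 0.20, *k* = 3: −1800 × 0.20 × 3/5 = −216. In the 1.0 arm, once feed has risen to 2160, later days that week read 2160 − 2016 = +144.
- Range: −36 (*r* = 0.10, *k* = 1) to −432 (*r* = 0.30, *k* = 4).

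**Null simulations.** Infection was independent of deficit. Two main settings were used:

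- Stays of 10–28 days, 6% daily noise, REE change lasting 7 days, previous-day deficit, Poisson regression with robust standard errors, 400 trials per scenario.
- 28 days, 8% daily noise, REE change starting the day after infection and lasting 14 days, the 10% dosing rule, Poisson GEE to first infection, 250 trials per scenario.

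Further runs varied the model and intake delivery. False-positive rates across the runs:

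| Deficit and model | No change | +10% | +20% |
|---|---|---|---|
| Weekly mean, arm included, intake as ordered | 5–7% | about 50–80% | 90–99% |
| Same, 20% day-to-day delivery variation (assumed) | – | 14–18% | 37–52% |
| Weekly mean, arm omitted, intake as ordered | 5–6% | 7–14% | 14–35% |
| Weekly mean, mean deficit to date, arm included | 9% | 40% | 85% |
| Latest reading on or before the day, arm included | 3–9% in all three columns | | |

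At 250 trials, the simulation error around a 5% rate is √(0.05 × 0.95/250) = 1.4 percentage points.

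In the second setting the median false rate ratio per 500 kcal/day of deficit was 3.99 at +10% and 9.79 at +20%. The fifth roots, 1.32 and 1.58 per 100 kcal/day, compare with 1.65 and 2.09 in the first setting. At −10% the ratio per 500 kcal/day was 0.29, with 72% false positives. If readings stopped after half of infections, as isolation for resistant organisms might cause, the rate at +20% was 64%.

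**The 28-day totals.** Averaging moves requirement between days of one week and, apart from weekend weighting, preserves the total. At +20%, the patient-level 28-day mean deficit gave a rate ratio of 1.40 with the weekly mean and 1.42 with each day's own requirement (false positives 11% and 10%). Averaging shifted infected against uninfected patients by about 1 kcal/day or less.

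**The case against.** The strongest reply has four parts.

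- **Aim 2a names 28-day cumulative and mean daily deficits.** These hardly change. This stands. A reader might infer that Aim 2a is corrupted as written, but the documents do not support that. The totals do include post-infection days; that is a separate problem of reverse causation, which weekly averaging does not cause.
- **Time-dependent use is permissive, and the plan fixes no lag, censoring rule or arm term beside the deficit.** This stands as a limit. It does not dispose of the point, because this is the only analysis text linking deficit to outcome.
- **The size rests on assumptions.** This stands. The documents do not say that infection raises REE; with no change there is no bias. Actual intake will also vary through tapering of parenteral feed, oral diet and calories from other infusions. With delivery variation of 10%, 20% and 30%, false positives in one set of runs fell from 64% to 36%, 18% and 12% at +10%, and from 99% to 80%, 52% and 28% at +20%. Isolation weakens the leak further.
- **A backward-looking requirement is not a full cure.** This also stands. If REE rises one day before the recorded infection date and feed follows a day later (both assumed), the latest-reading rule gave 89% and 99% false positives at +10% and +20%, against 80% and 99% for the weekly mean. With a two-day lead it gave 12–38%, against 4–7%. The lag therefore matters as much as the requirement rule.

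**Conclusion.** The point holds in a limited form. Post-infection readings enter the deficit of earlier days in the same week, and nothing in the plan prevents it. When the daily or to-date deficit is the time-dependent covariate and REE changes after infection, this can produce a false association, in either direction.

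The size depends on an assumed REE change, on how closely intake follows orders, and on whether arm is in the model. The simulated rates and rate ratios show direction and rough order, not expected trial results. It would be too strong to say that the plan will create a false link. The bias concerns timing within the week. The 28-day totals are almost unchanged, and the randomized comparison and the infection rates by arm do not use the deficit. The change is worth making before analysis, but it is not critical to the primary result.

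**What to change.** In Determination of energy deficit and in the Aim 1 analysis text, add a rule for any time-dependent use of the deficit:

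- Define each day's requirement from the latest cart reading on or before that day. Data Collection, item A, already uses the most recent reading when the cart is unavailable.
- Compute daily and to-date deficits from that series.
- Use the deficit only through a day before the infection date, and repeat with a longer lag as a sensitivity analysis because REE may change before infection is recorded.

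The weekly mean can stay for the 28-day totals. Feeding rules are untouched.

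The cost is one wording change and one reprogrammed derived variable, with no new measurements. Daily values become noisier, and carried-forward readings go stale during isolation or missed measurements, so the age of the reading should be reported.

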The increasing rate of hospital-acquired infection and sepsis are major causes of morbidity and mortality in intensive care unit (ICU) patients ^{1, 2}. The enormous impact of critical care-related illness demands that we find cost-effective therapies to improve outcome that can be rapidly implemented. Malnutrition is also very common in critically ill patients and is associated with increased hospital-acquired infections and mortality in ICU patients ³⁻¹³. Protein and/or energy deficits are associated with increased rates of hospital infection, skeletal muscle weakness, impaired wound healing, and prolonged convalescence in ICU patients ^{12, 14-17 3, 34-37}. To prevent or treat malnutrition, enteral nutrition EN and/or PN are routinely given worldwide to a significant proportion of ICU patients ³⁻¹³. **Unfortunately, very few well-designed RCTs on the clinical efficacy of specialized nutrition support modalities in critical illness have been performed** ^{18, 19}. Observational studies indicate that initial nutritional goals in ICU settings are infrequently achieved; recent surveys show that both underfeeding, and, to a lesser extent, overfeeding, are common in ICU settings ^{5, 7, 20-22}. Unfortunately, rigorous, prospective studies to determine effects of different energy doses have not been performed ^{5, 7, 12}. The comparative efficacy of energy doses in critically ill patients is thus unknown and clinical recommendations are conflicting and controversial; this issue is the focus of our application. Given the changes in the methods of ICU nutritional support during the past 5-10 years, including tighter blood glucose control ^{23, 24} and the use of overall lower caloric loads than in previous decades (when “hyperalimentation” was the norm), there is a clear need for further CER studies of different modalities of nutrition support based on current ICU clinical care practices ²⁵⁻³¹. Energy (calorie) needs in adult patients in the ICU often vary considerably because of day-to-day changes in clinical conditions ^{9, 32, 33}. However, optimal caloric requirements in critically ill patients are unknown due to a lack of rigorous RCTs. The resting energy expenditure (REE), or basal metabolic rate, is best determined using serial bedside metabolic cart measurements (indirect calorimetry), but technical issues (e.g. air leaks, high inspiratory oxygen concentration) can cause inaccuracies ^{3, 32, 33}. REE can also be estimated using standard equations, most commonly the Harris-Benedict equation (HBE), which incorporates the patient's age, gender, weight, and height ^{3, 10, 12}. Unfortunately, the HBE may over- or underestimate REE in critically ill patients ^{3, 32, 33}.

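### The inspired-oxygen limit for metabolic-cart readings is most likely written with its sign reversed

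*Combined protocol and SAP*

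**What the plan says.** The section on determination of energy deficit sets out when a cart reading is omitted on a given day. Apart from isolation for resistant organisms, there are three conditions:

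- inspired oxygen: "if the patient requires a fraction of inspired oxygen of < 60" (per cent);
- ventilator pressure: "has a requirement for positive end-expiratory pressure of > 12 cm" of water;
- leaks: "or has a documented leak in the ventilator or chest tube systems (precluding accurate cart measurements").

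The Background, discussing the same technique and citing the same two references (32 and 33), says that "technical issues (e.g. air leaks, high inspiratory oxygen concentration) can cause inaccuracies".

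The readings are used in several places. In Data Collection, item A, "The metabolic cart-derived REE will be used to determine basal energy expenditure (REE) and thus the initial energy dosing", and "MREE will be determined at baseline and 5x weekly". The hospital nutrition support section adjusts energy dosing from serial readings during the ICU stay. For Aim 2, "The daily energy deficit will be calculated by subtracting the calculated mean daily MREE" for the study week from actual intake. The Aim 2 statistical section compares cart readings with the Harris-Benedict estimate.

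**The concern.** An accuracy criterion should remove the readings that are likely to be wrong. The Background puts the oxygen-related error at high concentrations, but the operative rule bars low ones. Taken literally, a patient on 30% or 50% oxygen is not measured and a patient on 80% is.

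All three arms are defined as multiples of measured resting energy expenditure, so the readings are part of the intervention as well as an Aim 2 variable. If staff apply the text, doses would be set and adjusted from readings on the side the document itself distrusts. The weekly mean used for the energy deficit, and the agreement analysis against Harris-Benedict, would rest on the same readings.

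The only stated fallback, using the most recent measurement, covers an unavailable cart. It does not cover a patient barred by the oxygen criterion, who at baseline may have no earlier reading.

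**Working it through.** The plan gives no figure to reproduce. The check compares the relevant texts and then bounds the number of readings affected.

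**Direction of the limit**

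| Source of error | Background | Rule for omitting a reading | Agree? |
|---|---|---|---|
| Air leak | causes inaccuracy | a documented leak bars the reading | yes |
| Inspired oxygen | high concentration causes inaccuracy | below 60% bars the reading | no |
| Positive end-expiratory pressure | not mentioned | above 12 cm of water bars the reading | the high side is barred |

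The Background gives no percentage, so treating 60% and above as the high side is an inference. No section restates the oxygen limit or explains why low inspired oxygen would spoil a reading.

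**Fit with other plans**

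- Potential Risks describes hood measurements in patients off the ventilator. Patients needing no added oxygen could still be measured if the word requires is read to leave them out of the rule. Those on added oxygen below 60% could not.
- The Aim 2 analysis is stratified by ICU versus floor. The literal rule sits poorly with a floor stratum, but only by inference, because no oxygen figures are given for floor patients.

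**Bound on the number of readings**

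Inputs from the protocol: 60 patients; one baseline reading plus 5 per week; 28 days, or 4 weeks.

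- Readings per patient = 1 + 5 x 4 = 21.
- Ceiling = 60 x 21 = 1,260. The true number will be lower, because the adverse event section expects high morbidity and mortality and the other bars also apply.

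Let f be the share of readings below 60% oxygen. It is an assumption, since the documents give no distribution. Readings at exactly 60% are ignored.

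- Barred as written, first reading of the rule = 1,260 x f.
- Barred with the sign reversed = 1,260 x (1 - f).
- Barred as written, second reading (patients on no added oxygen fall outside the rule) = 1,260 x (f - g), where g is their share of all readings, assumed to be 0.2 and counted within f.

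| f (assumed) | As written, first reading | As written, second reading (g = 0.2) | Sign reversed |
|---|---|---|---|
| 0.3 | 378 | 126 | 882 |
| 0.5 | 630 | 378 | 630 |
| 0.7 | 882 | 630 | 378 |
| 0.9 | 1,134 | 882 | 126 |

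The two signs bar equal numbers when f = 1 - f, so f = 0.50. Under the second reading this occurs when f - g = 1 - f, so f = (1 + g)/2 = 0.60. Below these points the written rule bars fewer readings.

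One result holds for any f: among patients on added oxygen, every reading the written rule keeps is at 60% or more.

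**The case against.** The strongest counter-argument is practical. Item A assigns the readings to "a study team respiratory technician with prior experience and expertise in clinical indirect calorimetry", who may see the slip and ignore it. Item A also leaves nutrition unadjusted when a reading differs by less than 10% from the day before, which damps some errors. These points make the harm conditional. They do not correct the rule, and the 10% provision does not repair a wrong baseline reading. Relying on staff to depart from the protocol could also produce different practice at the two hospitals.

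A second objection is that the sign may have been misread when the PDF was converted. The greater-than sign in the same sentence survived, which makes this less likely but does not exclude it. The inclusion criteria contain another unexpected inequality (BMI above 40), which is a further reason to check the source.

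Third, the counts rest on assumed shares and measure readings lost, not validity. This stands: they bound the scale and do not by themselves show that the written rule is worse. The case rests on the conflict in the text.

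Fourth, the hood and floor points are weak, because neither section gives oxygen levels. That also stands; they are supporting only. Finally, the same-sentence comparison involves just one other numeric limit, since a leak is a yes-or-no condition. The conflict with the Background does not depend on that comparison.

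**Conclusion.** The concern holds. The rule for omitting cart readings contradicts the protocol's own account of what makes them inaccurate, and the most plausible explanation is a reversed sign. Confidence is high that the texts conflict. That the sign is reversed is an inference from the Background, the pressure limit and the absence of any stated reason for the opposite direction.

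The effect is directional only: the literal rule keeps readings on the side the document questions and drops others. How many are affected, within the ceiling of 1,260, cannot be known from the documents, nor can the resulting error in dose or deficit. Actual harm depends on whether staff follow the text. It should be fixed, because the measurement underlies both the dosing and Aim 2.

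**What to change.** First check the sign in the source file. If it stands as printed here, amend the sentence on determination of energy deficit so that this measurement-validity criterion excludes the high-oxygen readings the Background describes. Confirm that the result is consistent with the hood measurements under Potential Risks and the ICU and floor strata in the Aim 2 analysis. The 60% cut-point can stay as it is.

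The cost is a one-character amendment, with no extra patients, staff or procedures.
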